Several stratified analyses will be conducted. PPSV23 is recommended for PLWH and feasibility data provided by Komodo suggest that one in four PWLH who received PCV13 during 2014-2015 also received PPSV23 within two years. Rather than censor or exclude

individuals who receive PPSV23, we will calculate PCV13 VE among PWLH who have/have not received PPSV23 before and during the study period.

Feasibility assessments from Komodo indicate that approximately 25% of PWLH have at least one CD4 cell count or percentage laboratory result available. Therefore, we will calculate PCV13 VE among the subset of PWLH who have a CD4 cell count during the baseline period or follow-up, and potentially stratify by CD4 category using each patient's lowest value during the study.

Additional VE stratifications by ART adherence during follow-up, year of HIV diagnosis, and age will be assessed for feasibility as well, as these affect patients' immune status and immune reconstitution. Due to possible waning of the VE and different lengths of follow-up by index year, VE stratification by year of HIV diagnosis will be restricted to the first 3 years of follow-up.

A sensitivity analysis will also be conducted. In this analysis, causes of pneumonia that are characteristic of HIV, for example pneumonia due to cytomegalovirus, mycobacteria, and fungi, will be excluded from our definition of all-cause pneumonia.

Residual confounding of our VE estimates due to inadequate control for health care seeking behavior and immune status in our analyses will be explored. To do so, we will employ a negative control exposure and a negative control outcome. Potential negative control exposures include vaccinations that are recommended for PLWH but would not be expected to have any protective effect against the pneumonia outcomes of interest. If residual confounding does not exist, the negative control vaccine would not have an effect on the pneumonia outcomes. However, if the analysis demonstrates that the negative control vaccine protects against these outcomes, this suggests the presence of residual confounding.

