16. APPENDIX

Table 1. Diagnosis Codes for Identifying HIV infection

Code	Type	Description
042	ICD-9-CM	HIV-1 infection
V08	ICD-9-CM	Asymptomatic HIV disease
B20	ICD-10-CM	HIV-1 infection
Z21	ICD-10-CM	Asymptomatic HIV disease

Table 2. National Drug Codes for Identifying HIV Antiretrovirals (see excel)

Table 3. National Drug Codes and CPT® Codes for Identifying PCV13 Vaccination

Code	Type	Description
50090194409	NDC	13-valent pneumococcal conjugate vaccine
54569661300	NDC	13-valent pneumococcal conjugate vaccine

PFIZER CONFIDENTIAL

CT24-WI-GL02-RF02 5.0 Non-Interventional Study Protocol Template For Secondary Data Collection Study

01-Aug-2023

Page 29 of 46

50090194400	NDC	13-valent pneumococcal conjugate vaccine
00005197105	NDC	13-valent pneumococcal conjugate vaccine
00005197104	NDC	13-valent pneumococcal conjugate vaccine
00005197102	NDC	13-valent pneumococcal conjugate vaccine
00005197101	NDC	13-valent pneumococcal conjugate vaccine
90670	CPT	13-valent pneumococcal conjugate vaccine

Table 5. Diagnosis Codes for Identifying Pneumococcal Pneumonia and Pneumonia with Unspecified Causes

Condition	ICD-9-CM		ICD-10-CM	
	Codes	Description	Codes	Description
Pneumococcal pneumonia	481	Pneumococcal pneumonia	J13	Pneumonia due to Streptococcus pneumoniae
	482.9 + 041.2	Bacterial pneumonia, unspecified + pneumococcus	J15.9 + B95.3	Unspecified bacterial pneumonia + Streptococcus pneumoniae
	485 + 041.2	Bronchopneumonia, organism unspecified + pneumococcus	J18.0 + B95.3	Bronchopneumonia, unspecified organism + Streptococcus pneumoniae
	486 + 041.2	Pneumonia, organism unspecified + pneumococcus	J18.8 + B95.3 J18.9 + B95.3	Other pneumonia, unspecified organism + Streptococcus pneumoniae Pneumonia, unspecified organism + Streptococcus pneumoniae
	510.x + 041.2			Empyema + pneumococcus
	510 + 041.2	Empyema with fistula + pneumococcus	J86.0 + B95.3	Pyothorax with fistula + Streptococcus pneumoniae
	510.9 + 041.2	Empyema without mention of fistula + pneumococcus	J86.9 + B95.3	Pyothorax without fistula + Streptococcus pneumoniae
Pneumonia with unspecified causes	480-486 487.0			Viral, bacterial, unspecified pneumonia
	480.9	Viral pneumonia, unspecified	J12.9	Viral pneumonia, unspecified
	482.9	Bacterial pneumonia, unspecified	J15.9	Unspecified bacterial pneumonia
	485	Bronchopneumonia, organism unspecified	J18.0	Bronchopneumonia, unspecified organism

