	486	Pneumonia, organism unspecified	J18.8 J18.9	Other pneumonia, unspecified organism Pneumonia, unspecified organism

PFIZER CONFIDENTIAL

CT24-WI-GL02-RF02 5.0 Non-Interventional Study Protocol Template For Secondary Data Collection Study 01-Aug-2023

Page 31 of 46

Table 4. Diagnosis Codes for Identifying Invasive Pneumococcal Disease, All-Cause Pneumonia, and Pneumococcal Pneumonia

Condition	ICD-9-CM		ICD-10-CM	
	Codes	Description	Codes	Description
IPD				
Bacteremia	790.7 + 041.2 771.83 + 041.2	Bacteremia + pneumococcus	R78.81 + B95.3	Bacteremia + Streptococcus pneumoniae as the cause of diseases classified elsewhere (Streptococcus pneumoniae)
	038.2	Pneumococcal septicemia	A40.3	Sepsis due to Streptococcus pneumoniae
	038.9 + 041.2	Unspecified septicemia + pneumococcus	A41.9 + B95.3	Sepsis, unspecified organism + Streptococcus pneumoniae
Meningitis	320.1	Pneumococcal meningitis	G00.1	Pneumococcal meningitis
	320.9 + 041.2	Meningitis due to unspecified bacterium + pneumococcus	G00.9 + B95.3 G04.2 + B95.3	Bacterial meningitis, unspecified + Streptococcus pneumoniae Bacterial meningoencephalitis and meningomyelitis, not elsewhere classified + Streptococcus pneumoniae
	322.9 + 041.2	Meningitis, unspecified + pneumococcus	G03.9 + B95.3	Meningitis, unspecified + Streptococcus pneumoniae
Other	421.x + 041.2	Endocarditis + pneumococcus		
	421 + 041.2	Acute and subacute bacterial endocarditis + pneumococcus	I33.0 + B95.3	Acute and subacute infective endocarditis + Streptococcus pneumoniae
	421.1 + 041.2	Acute and subacute infective endocarditis in diseases classified elsewhere + pneumococcus	I39 + B95.3	Endocarditis and heart valve disorders in diseases classified elsewhere + Streptococcus pneumoniae
	421.9 + 041.2	Acute endocarditis, unspecified + pneumococcus	I33.9 + B95.3	Acute and subacute endocarditis, unspecified + Streptococcus pneumoniae
	711.0 + 041.2	Septic arthritis + pneumococcus	M00.00 + B95.3 M00.20 + B95.3 M00.80 + B95.3 M00.9 + B95.3 M00.10 + B95.3	Staphylococcal arthritis, unspecified joint + Streptococcus pneumoniae Other streptococcal arthritis, unspecified joint + Streptococcus pneumoniae Arthritis due to other bacteria, unspecified joint + Streptococcus pneumoniae Pyogenic arthritis, unspecified + Streptococcus pneumoniae Pneumococcal arthritis, unspecified joint + Streptococcus pneumoniae

PFIZER CONFIDENTIAL

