### 5.3. Variables

#### 5.3.1. Effectiveness Endpoints

The outcomes of interest for the primary and secondary objectives are listed in Table 5.2.

Episodes separated by at least 90 days will be considered independent events. For claims that include pneumonia that are separated by <90 days, those claims will be collapsed into a single episode with a date of the initial diagnosis.

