**Table 5.2 Outcomes of Interest**

Outcome Type	Outcome	Definition
Primary outcomes	IPD	ICD-9-CM or ICD-10-CM codes listed in Appendix Table 7.4
	Pneumococcal pneumonia	ICD-9-CM or ICD-10-CM codes listed in Appendix Table 7.4
	All-cause pneumonia	ICD-9-CM or ICD-10-CM codes listed in Appendix Table 7.4
Secondary outcomes	Pneumococcal pneumonia or pneumonia with unspecified causes	ICD-9-CM or ICD-10-CM codes listed in Appendix Table 7.5
	Pneumonia with unspecified causes	ICD-9-CM or ICD-10-CM codes listed in Appendix Table 7.5
Sensitivity analysis outcome	All-cause pneumonia not associated with HIV	ICD-9-CM or ICD-10-CM codes listed in Appendix Table 7.6

For combination diagnosis codes, (e.g., bacteremia + pneumococcus) for diagnoses in an inpatient setting patients must have all codes within the same admission. The latest date of the combination of diagnoses will be used as the diagnosis date. For diagnoses in an outpatient setting patients must have all codes within the same date.

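### No rule covers events that also carry an excluded-cause code, so pneumococcal events can count as unspecified-cause pneumonia and mixed HIV-characteristic events stay in the sensitivity outcome

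*Protocol*

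**What the plan says.** Protocol 9.7 describes one sensitivity analysis: causes characteristic of HIV, with "pneumonia due to cytomegalovirus, mycobacteria, and fungi" given as examples, "will be excluded from our definition of all-cause pneumonia". SAP Table 5.2 calls the result "All-cause pneumonia not associated with HIV" and defines it as "ICD-9-CM or ICD-10-CM codes listed in Appendix Table 7.6". The secondary outcome of unspecified-cause pneumonia is defined in the same way, as "ICD-9-CM or ICD-10-CM codes listed in Appendix Table 7.5". Protocol Appendix Tables 5 and 11 carry the same lists as SAP Tables 7.5 and 7.6.

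Within Protocol Appendix Table 5, the pneumococcal rows include "J18.8 + B95.3 J18.9 + B95.3", while the unspecified-cause rows accept the same base codes on their own ("Other pneumonia, unspecified organism Pneumonia, unspecified organism").

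SAP 5.3.1 has two rules on multiple claims. Pneumonia claims less than 90 days apart are merged: "those claims will be collapsed into a single episode with a date of the initial diagnosis". For combination codes, all parts must fall in the same admission (inpatient) or on the same date (outpatient), and the latest date is used. Protocol 9.8 adds that variables other than demographics are defined by the presence of specific data such as diagnosis codes.

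**The concern.** Both outcomes are meant to leave something out: known causes in one, HIV-characteristic causes in the other. The lists do this by omitting codes. Omitting a code stops it from qualifying an event, but it does not stop another code on the same admission or claim date from qualifying that event.

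Secondary objective 2 would therefore report a VE for unspecified causes that includes events coded as pneumococcal, and possibly others with a named organism. The bias can go either way: pneumococcal events would tend to raise the VE, and causes that PCV13 does not prevent would lower it.

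The sensitivity analysis is useful because Protocol 9.7 itself calls immune status an important predictor of pneumonia and says CD4 values will be missing for most of the cohort. Mixed events that stay in pull its result toward the main all-cause result, so agreement between the two is partly built in.

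**Working it through.** The plan states no figure on this point, so there is none to reproduce. The check compares the code lists and then gives an illustration of size.

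**1. Pneumococcal against unspecified rows, SAP Table 7.5** (510.x + 041.2 is a group heading and is not counted)

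- ICD-9-CM, 6 pneumococcal definitions: 481; 482.9, 485, 486, 510 and 510.9, each + 041.2. The base code of three (482.9, 485, 486) qualifies alone as unspecified.
- ICD-10-CM, 7 definitions: J13; J15.9, J18.0, J18.8, J18.9, J86.0 and J86.9, each + B95.3. The base code of four (J15.9, J18.0, J18.8, J18.9) qualifies alone as unspecified.
- Overlap: 3 of 6 plus 4 of 7 = 7 of 13. No extra claim is needed for these. The two outcomes may also be dated differently within one admission, because a combination takes its latest date and a merged episode its first.

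**2. SAP Table 7.4 (all-cause) against Table 7.6 (sensitivity)**

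- Dropped: 483/J15.7, 484.1/B25.0, 484.6/B44.0, 484.7 and 136.3/B59.
- Kept: all five ICD-10-CM unspecified codes (J12.9, J15.9, J18.0, J18.8, J18.9). An admission with J18.9 and B59 therefore still has a qualifying code.

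**3. Search for a rule that disqualifies.** The 90-day rule merges and dates claims but assigns no cause. The combination rule only builds qualifying events. SAP Table 5.3 takes Pneumocystis codes out of the follow-up opportunistic-infection covariate when all-cause pneumonia is analysed, so the overlap was noticed for a covariate, but no matching rule exists for outcomes.

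**4. Illustration for the sensitivity outcome.** The documents give neither input, so both are assumptions: p, the HIV-characteristic share of all-cause events, 5% to 15%; and f, the share of those that also carry an unspecified code, 50% to 80%. Deleting codes removes p(1 − f) and leaves pf, so the residual share is

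m = pf / [1 − p(1 − f)]

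- p = 5%, f = 50%: 0.025 / 0.975 = 2.6%
- p = 10%, f = 80%: 0.08 / 0.98 = 8.2%
- p = 15%, f = 80%: 0.12 / 0.97 = 12.4%

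Observed VE is approximately (1 − m) × VE in target events + m × VE in the others, with m taken among unvaccinated events. With zero VE in the others and the 5% and 15% that Protocol 9.5 assumes for all-cause pneumonia:

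- m = 2.6%: 0.974 × 15% = 14.6%; 0.974 × 5% = 4.9%
- m = 12.4%: 0.876 × 15% = 13.1%; 0.876 × 5% = 4.4%

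**5. Illustration for the unspecified-cause outcome.** Assume m from 2% to 30% and a target VE of 5%.

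- Misplaced events pneumococcal, with VE 22.5% (borrowed from the upper IPD assumption in Protocol 9.5, which gives none for pneumococcal pneumonia): 0.98 × 5% + 0.02 × 22.5% = 5.4%, up to 0.70 × 5% + 0.30 × 22.5% = 10.3%.
- Misplaced events not preventable by PCV13: 0.98 × 5% = 4.9%, down to 0.70 × 5% = 3.5%.

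**6. Table 7.6 against Protocol 9.7**

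- 484.7 (other systemic mycoses) is dropped, but J17, which Table 7.4 pairs with both 484.7 and 484.8, stays. The two coding eras therefore differ.
- The heading range 480-486, read literally, covers the dropped 483 and 484.x codes. The same range heads the unspecified-cause rows of Table 7.5, where it would cover 481.
- The protocol names mycobacteria. The lists contain no mycobacterial code, and a Mycoplasma row (483/J15.7) is dropped.

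**The case against.** The documents are silent on mixed events; they never say that such events count. Table 7.5 lists pneumococcal and unspecified-cause pneumonia as separate conditions, and secondary objective 1 joins them with 'or', which fits an intended partition. That is fair as to intent, but the SAP gives a programmer only presence-based lists, and those put the event in both sets.

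A reader might infer that neither outcome measures what its name says. The documents do not support that: events with only an unspecified code are classified as intended, and in the sensitivity outcome known causes not characteristic of HIV are meant to stay. A reader might also infer that most HIV-characteristic events survive the exclusion. That follows only from the assumed f. Nor is it informative that every pneumococcal event defined by an unspecified code is counted twice, since that is true by construction and does not give the pneumococcal share of unspecified-cause events.

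The illustrated shifts for the sensitivity outcome are modest. They lie within the planned all-cause intervals in Protocol Table 3 (4% annual censoring: 11 to 19 and 1 to 9 at 36 months, 13 to 17 and 2 to 7 at 97 months). Protocol 9.7 states no purpose for the sensitivity analysis, and immune status is also addressed through opportunistic infections and ART adherence as covariates, a possible candidiasis negative control outcome and the CD4 subset. All of this stands. It limits the weight of the point but does not supply the missing rule.

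Excluding over the whole 90-day episode would also be open to criticism: a code recorded up to 89 days later would delete an event dated to the initial diagnosis. That objection is accepted, and the fix avoids it.

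**Conclusion.** The point holds as a gap in two outcome definitions. Applied as written, the lists put every event meeting 7 of the 13 pneumococcal definitions into the unspecified-cause outcome, and they keep in the sensitivity outcome any event with an unspecified code alongside B59, B25.0 or B44.0. This rests on reading SAP Table 5.2 literally, together with the absence of any disqualifying rule.

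The reach is limited. The three primary outcome definitions are unaffected. The composite secondary outcome is not harmed by the pneumococcal overlap, though events with another known cause can still enter it. The effect on VE cannot be derived from the documents, and the figures above are illustrations on assumed inputs. The gap should be closed before the outcome flags are programmed; it does not threaten the main conclusions.

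**What to change.** Add to SAP 5.3.1, using the window already set there for combination codes (same admission if inpatient, same date if outpatient):

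1. Sensitivity outcome: do not count an event if an HIV-characteristic code removed from Table 7.6 is present.
2. Unspecified-cause outcome: count an event only if no organism-specific pneumonia code and no 041.2 or B95.3 is present. An unspecified code + 041.2 or B95.3 is classified as pneumococcal only.

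Report how many events each rule reclassifies. Exclusion over the full 90-day episode should be at most a check, because it classifies events by later codes.

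Also reconcile Table 7.6 (and Protocol Appendix Table 11) with Protocol 9.7: decide on J17, state whether the range 480-486 is a label or a definition (in Table 7.5 too), and settle whether mycobacteria or Mycoplasma was meant.

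The cost is a few sentences and two outcome flags reprogrammed from claims already held. There will be slightly fewer events in both outcomes, and some true mixed infections will be lost. The narrow window will also miss an outpatient J18.9 claim a few days before or after an admission coded B59; the 90-day check would show how often that happens.

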9. RESEARCH METHODS

9.1. Study Design

The VE study will be a retrospective cohort study using health care administrative claims and laboratory data (Figure 1).

PLWH will be identified using administrative claims and include individuals with at least one inpatient International Classification of Diseases, Ninth Revision, Clinical Modification (ICD-9-CM) or International Classification of Diseases, Tenth Revision, Clinical Modification (ICD-10-CM) code related to HIV (Appendix Table 1) or at least 2 outpatient ICD-9-CM or ICD-10-CM codes related to HIV at least 30 days, but no more than 730 days apart, during January 1, 2014 and

PFIZER CONFIDENTIAL

December 31, 2021. PLWH are required to have at least six months of continuous enrollment in one or more health plans and pharmacy benefits after their first HIV-related ICD-9-CM or ICD-10-CM code. These six months of continuous enrollment will be considered the baseline period, during which baseline covariates including demographics, comorbidities, and preventative care will be measured. The baseline period was also selected to minimize the number of outcome events that existed prior to or triggered an HIV diagnosis.

The date following the last date of the baseline period will be defined as the index date. The end of the study will occur on the last date that administrative claims data will be available, September 30, 2022.

For PLWH who receive PCV13 after their index date, we will include the time between their index date and the 13 days after their PCV13 vaccination date as unvaccinated follow-up time. Any outcomes occurring during this time will be counted as events in the unvaccinated cohort. Follow-up that occurs 14 days or more after PCV13 vaccination will be defined as vaccinated follow-up time.

Unvaccinated (no PCV13) PLWH will be followed from index date until the earliest occurrence of the following: 13 days after PCV13 vaccination, death, end of health plan enrollment, or end of study period. Vaccinated PLWH will be followed from 14 days after their PCV13 vaccination, or index date if they were vaccinated during the baseline period, until the earliest occurrence of the following: death, end of health plan enrollment, or end of study period.

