9.2.1. Inclusion Criteria

To be eligible for the vaccine effectiveness study, individuals must meet the following criteria:

1. HIV infection defined as at least one inpatient International Classification of Diseases, Ninth Revision, Clinical Modification (ICD-9-CM) or International Classification of Diseases, Tenth Revision, Clinical Modification (ICD-10-CM) code related to HIV (Appendix Table 1) or ≥ 2 outpatient ICD-9-CM or ICD-10-CM codes related to HIV at least 30 days, but no more than 730 days apart, during January 1, 2014 and December 31, 2021

AND

2. At least 18 years of age at the time of the first recording of HIV-related ICD-9-CM or ICD-10-CM code

PFIZER CONFIDENTIAL

CT24-WI-GL02-RF02 5.0 Non-Interventional Study Protocol Template For Secondary Data Collection Study 01-Aug-2023

AND

[figure not shown]
3. At least six months of continuous enrollment in medical and pharmacy plans after the first HIV-related ICD-9-CM or ICD-10-CM code between January 1, 2014 and December 31, 2021. A gap of 30 days or less in enrollment will be allowed during this six month period.

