9.5. Study Size

The planned analyses do not involve hypothesis testing and sample size calculations are not applicable. However, we examined the precision of PCV13 vaccine effectiveness for IPD and all-cause pneumonia among people living with HIV at 36 months and 97 months (which was the maximum follow-up time available from feasibility assessments) after index (Table 2 and Table 3). Komodo Health provided the following information for the precision estimates:

- 175,000 individuals had ≥ 1 inpatient or ≥ 2 outpatient HIV ICD-9-CM or ICD-10-CM code diagnosis codes between January 1, 2014 and December 31, 2021
- 56,000 (32%) of these individuals received PCV13 after their first HIV diagnosis code

The following assumptions regarding incidence and PCV13 VE for IPD and all-cause pneumonia were used:

- IPD incidence among PLWH is 183 cases per 100,000 population [28]
- All-cause pneumonia incidence among PLWH is 5,487 cases per 100,000 population
- VE for IPD due to any serotype ranges from 7.5% to 22.5%
 - Published VE estimates for vaccine type IPD range from 25% to 75% [20]. Because one-third of the adult IPD burden is considered PCV13 type [29], we multiplied this range by 30% to arrive at 7.5% to 22.5%
- VE for all-cause pneumonia ranges from 5% to 15% [30]
- Annual censoring of individuals due to loss to follow-up or death may range between 4% or 10%

Survival and censoring times were simulated assuming exponential distributions. Vaccination status was modelled as a time-varying covariate [31]. Hazard ratios were assumed as $1 - (VE/100)$. Simulations were run 100 to 200 times per scenario. Cox regression models were run on each simulated dataset to estimate the 95% confidence

PFIZER CONFIDENTIAL

intervals (CI) for the log HRs. Means were generated and exponentiated to obtain the 95% CIs for the VEs using $(1 - HR) \times 100$ and used to describe VE precision.

Table 2. Precision of PCV13 vaccine effectiveness estimates for invasive pneumococcal disease

Hypothesized Vaccine Effectiveness (%)	36 months of follow-up			97 months of follow-up		
	Lower 95% confidence interval estimate	Upper 95% confidence interval estimate	Total number of events	Lower 95% confidence interval estimate	Upper 95% confidence interval estimate	Total number of events
Scenario #1 – 4% annual censoring						
7.5	-12	25	837	-5	19	1492
22.5	3	37	817	11	33	1452
Scenario #2 – 10% annual censoring						
7.5	-15	25	766	-6	21	1272
22.5	2	38	752	9	33	1224

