Similarly, potential negative control outcomes are outcomes that share the same sources of biases as the primary outcomes in our study population but are not causally-related to PCV13 vaccination. For example, immune status is an important predictor of pneumonia outcomes among PLWH, but we will be missing CD4 laboratory values for most of our study population. In order to detect potential residual confounding by lack of control for immune status, a potential negative control outcome could include a more common AIDS defining illness such as candidiasis. Again, if no residual confounding exists, PCV13 vaccination would have no effect on the occurrence of the negative control outcomes. However, if the results suggest that PCV13 vaccination prevents the negative control outcomes, residual confounding may exist.

Detailed methodology for summary and statistical analyses of data collected in this study will be documented in a statistical analysis plan (SAP), which will be dated, filed and maintained by the sponsor. The SAP may modify the plans outlined in the protocol; any major modifications of primary endpoint definitions or their analyses would be reflected in a protocol amendment.

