### 5.3.2. Covariates

The list of demographic and clinical characteristics considered for descriptive reporting, subgroups and inclusion as covariates in models for generating the propensity scores are provided in Table 5.3. The Komodo Health database will be source of all variables.

Patients will be considered to have a comorbidity or hospitalization during baseline if there was evidence of a diagnosis at any time during the baseline period. Evidence of comorbidities or hospitalization during follow-up will be considered as new diagnoses. Once diagnosed, patients will be considered diagnosed for the remainder of their follow-up. ART adherence during baseline and follow-up will be updated every 6 months (180 days) based on the data collected in that previous timeframe. For baseline annual physical exam and annual influenza vaccine, patients will be considered adherent (coded as 'Yes') if there was evidence of these events at any time during the baseline period. During the follow-up, patients will be considered adherent up to 365 days after the last event date.

For annual CD4 and viral load laboratory tests during baseline and follow-up, patients will be coded as 'Yes' up to 365 days after the last event date. For respiratory virus season during follow-up, patients will be coded as 'Yes' if the observation time is in October, November, December, January, February, March or April.

The baseline period for the assessment of covariates is the six months prior to the index date, i.e., no data prior to six months will be included.

Covariates used at baseline only will be considered time-fixed confounders. Covariates additionally or only used during follow-up will be considered time-varying confounders.

Categories may be collapsed, or covariates may be excluded from the propensity scores if models fail to converge.

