### 7.3. Appendix C: Diagnosis and Procedure Codes Used in the Study

**Table 7.1 Diagnosis Codes for Identifying HIV Infection**

Code	Type	Description
042	ICD-9-CM	HIV-1 infection
V08	ICD-9-CM	Asymptomatic HIV disease
B20	ICD-10-CM	HIV-1 infection
Z21	ICD-10-CM	Asymptomatic HIV disease

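### The cohort-defining HIV codes carry a crude marker of disease stage that no covariate list uses, although CD4 results exist for only about a quarter of patients

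*Protocol*

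**What the plan says.** **CD4.** Protocol 9.7 reports from the feasibility work that "approximately 25% of PWLH have at least one CD4 cell count or percentage laboratory result available". In the rationale for the negative control outcome it names immune status as an important predictor and adds that "we will be missing CD4 laboratory values for most of our study population". Protocol Table 1 lists the CD4 value among the covariates, but SAP Table 5.3 gives it a descriptive and subgroup role only, so it does not enter the propensity models.

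**HIV codes.** Protocol Appendix Table 1 and SAP Table 7.1 define HIV infection by four codes. 042 and B20 are labelled "HIV-1 infection"; V08 and Z21 are labelled "Asymptomatic HIV disease". The first inclusion criterion requires at least one such inpatient code or two outpatient codes. Enrollment is counted from the first HIV code, and Protocol 9.1 says: "These six months of continuous enrollment will be considered the baseline period".

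**Adjustment set.** SAP 5.3.2 introduces Table 5.3 as "The list of demographic and clinical characteristics considered for descriptive reporting, subgroups and inclusion as covariates" in the propensity models. The entries closest to HIV severity are opportunistic infections, ART adherence, hospitalization, and whether a CD4 or viral load test was done in the past year. HIV code type is not in Table 5.3, Protocol Table 1 or the covariate list in Protocol 9.7.

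**The concern.** The plan identifies immune status as a gap in its confounding control, yet leaves unused a piece of HIV-specific information that the cohort definition already extracts. If code type tracks disease stage even loosely, it could be related both to the outcomes and to the chance of receiving PCV13. Part of that relation may not be captured by the covariates in the plan.

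This matters most for all-cause pneumonia. The anticipated VE is small (5% to 15%) and the planned intervals are narrow, so a modest bias could rival the random error, and a larger sample would not reduce it.

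**Working it through.** **1. CD4 coverage.** "175,000 individuals had ≥ 1 inpatient or ≥ 2 outpatient HIV ICD-9-CM or ICD-10-CM code diagnosis codes" (Protocol 9.5).
- With a result: 0.25 × 175,000 = 43,750. Without: 0.75 × 175,000 = 131,250.
- 43,750 corresponds to the N/4 row of SAP Table 5.1 (43,000). There the best-case 95% interval is -5% to 41% for IPD and 10% to 20% for all-cause pneumonia.
- SAP 5.2.3 runs a subgroup only where the best-case interval is expected to exclude zero. The CD4 subset meets that rule for all-cause pneumonia but not for IPD.

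**2. Availability of code type.** The first HIV code opens the six months that end at index, so each patient has at least one of the four codes by then. A patient can carry both types, so a classification rule is needed.

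**3. Illustration of size.** The documents give neither the prevalence of each code type by vaccination status nor a code-specific risk, so every input in this step except the VE values is an assumption:
- 50% prevalence of 042/B20 in the lower-prevalence group
- an imbalance d of 3, 5 or 10 points remaining after the planned adjustment
- an outcome risk ratio RR of 1.5, 2 or 2.5, conditional on the planned covariates

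For a binary marker left out of the model, the HR is multiplied by k when the vaccinated have the higher prevalence, and divided by k when the unvaccinated do:

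k = [1 + (0.50 + d)(RR - 1)] / [1 + 0.50(RR - 1)]

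| Case | k | VE if the vaccinated carry more 042/B20: 1 - 0.85k | VE if they carry less: 1 - 0.85/k |
|---|---|---|---|
| d = 0.03, RR = 1.5 | 1.265/1.25 = 1.012 | 14.0% | 16.0% |
| d = 0.05, RR = 2 | 1.55/1.50 = 1.033 | 12.2% | 17.7% |
| d = 0.10, RR = 2.5 | 1.90/1.75 = 1.086 | 7.7% | 21.7% |

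(True all-cause VE of 15%, so true HR = 0.85.)

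**4. Against random error.** Protocol Table 3 gives 13% to 17% (4% annual censoring) or 12% to 18% (10%) for a VE of 15% at 97 months. The smallest shift lies inside those intervals. The middle case lies inside the wider one and outside the narrower one, and the largest lies outside both.

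For IPD at a true VE of 22.5%, the two extreme k values give 0.775 × 1.086 = 0.841 (VE 15.9%) and 0.775/1.086 = 0.714 (VE 28.6%). Both are inside the 11% to 33% of Protocol Table 2 (97 months, 4% censoring).

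**5. Against the balance threshold.** SMD = d / √{[p₁(1 - p₁) + p₀(1 - p₀)]/2}. With 50% in one group, 3, 5 and 10 points give about 0.06, 0.10 and 0.20. SAP 5.8.5 treats an SMD up to 0.1 as negligible, so the largest case would be flagged if code type were in the balance table. At present it is not.

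**The case against.** The strongest case on the other side has four parts.

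- **The split is not a documented stage marker.** Neither document calls 042/B20 symptomatic, advanced or AIDS, and neither validates the distinction. Protocol 9.9 concedes that HIV codes may be used when ordering tests to rule out infection. A reader might infer that true disease stage is known for the whole cohort. The documents support only that each patient has at least one of four codes. This stands.
- **Immune status is not left unadjusted.** Opportunistic infections (a list widened in protocol version 3.0), ART adherence updated every 180 days, hospitalization, previous pneumonia and immunosuppressive medication are all covariates. There is also a CD4-subset analysis and a candidiasis negative control with optional bias correction. This largely stands, with limits: test-done indicators measure care-seeking rather than stage, Pneumocystis codes are dropped from the follow-up opportunistic-infection covariate for all-cause pneumonia, and a negative control detects confounding but does not replace adjusting for information already held. What code type adds beyond these covariates cannot be judged from the documents; the opportunistic-infection code list is in a separate file.
- **The size is wholly assumed.** The risk ratio would have to hold after conditioning on the existing covariates, and a 10 point residual imbalance is twice the plan's own threshold. This stands: the figures show what could happen, not what will.
- **A covariate can do harm.** A time-varying indicator that stays on once triggered could be set by a 042/B20 code recorded at a pneumonia encounter. Lagging helps for first events, but in the recurrent-event analysis the indicator could follow from an earlier outcome. This stands against a time-varying version in the main model. It does not apply to an indicator fixed at baseline.

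**Conclusion.** The plan omits an inexpensive, HIV-specific proxy that every patient has by index, on a factor it says it cannot measure for most of the cohort. The omission may leave some avoidable confounding by immune status beyond what the planned covariates remove. This makes the point a worthwhile improvement, not a demonstrated bias.

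The shift of about 1 to 7 VE points at a true all-cause VE of 15% rests entirely on the assumed prevalence, imbalance and risk ratio, and its direction is unknown. A reader might infer that all three primary VE estimates are biased by a known amount. The documents do not support that: they contain none of the inputs needed, and for IPD even the largest assumed case stays within the planned interval.

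**What to change.** 1. Add to SAP Table 5.3 a time-fixed baseline covariate, HIV code type: any 042/B20 versus only V08/Z21 during the six-month baseline, counting the first HIV code that opens it.
2. Include it in the numerator and denominator of the IPTW and IPCW models and, as SAP 5.8.7 requires for time-fixed covariates, in the Cox-MSM. Because it is in both numerator and denominator, most of the adjustment comes from the outcome model.
3. Report its SMD before and after weighting. For the reason in item 2, the weights alone need not bring the SMD to zero.
4. Cross-tabulate it against CD4 category in the roughly 25% with results, to show whether it carries stage information.
5. Use a time-varying version only as a sensitivity analysis, lagged like the other time-varying covariates and ignoring codes recorded on outcome encounters.
6. If the covariate is not adopted, state the reason in the SAP.

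**Cost.** One derived variable from codes already extracted. Coding habits may differ between providers, so the marker is noisy and may slightly widen the weights. SAP 5.3.2 already allows a covariate to be dropped if the models fail to converge.
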